### 8.5.2 Safety Monitoring and Permanent Stopping Rules for Renal Function

All patients will have renal function tests monitored monthly during the Treatment Period. Upon completion of the study Treatment Period, renal function tests should be monitored during the Post-Treatment Follow-Up Period as per visit schedule in [Appendix A](#).

Renal function surveillance will include serum creatinine and urinalysis including UACR and UPCR. The assessment of serum creatinine and urinalysis more frequently than monthly will be guided by the Sponsor Medical Monitor or designee.

All renal function test results will be reviewed on an ongoing basis at the safety review by the Sponsor Medical Monitor or designee.

All lab alerts for renal function tests must be promptly reviewed by the Investigator (within 2 business days of receipt) and Medical Monitor(s) according to the Medical Data Surveillance Plan.

In the event of appearance of symptoms or signs consistent with renal dysfunction such as hematuria, polyuria, anuria, flank pain, new-onset hypertension, nausea and/or anorexia, renal function should be tested as soon as possible (ideally within 3 days). Testing at a lab that is local to the patient is permissible for this purpose.

If any of the below criteria are met,

- eGFR (by CKD-EPI formula) decrease from Baseline  $> 40\%$
- UPCR  $> 1000 \text{ mg/g}$
- UACR  $> 600 \text{ mg/g}$

and the initial measurement(s) is confirmed (as described in Confirmation Guidance above) the following steps should be taken:

1. The Study Drug must be paused
2. Further investigations into the cause of renal function abnormalities should be performed. These may include review of patient's prior and concurrent diseases and procedures, concomitant medications for potentially nephrotoxic agents, and search for potential pre-renal causes.
3. Patients having alternative etiology identified that may account for abnormal renal results may restart treatment with Study Drug when:
  - a. Lab values have improved to:
    - eGFR decrease < 40% from baseline, and/or
    - UPCR < 1000 mg/g, and/or
    - UACR < 600 mg/g, and
  - b. Study Medical Monitor or designee has approved Study Drug treatment to restart
4. Patients without identified alternative etiology for renal function abnormalities may restart Study Drug Treatment when:
  - a. Lab values have improved to:
    - eGFR decrease < 20% from baseline, and/or
    - UPCR < 500 mg/g, and/or
    - UACR < 300 mg/g, and
  - b. Study Medical Monitor or designee has approved Study Drug treatment to restart
5. Patients without alternative explanation for renal function abnormalities and **meeting any of the following criteria must have Study Drug stopped permanently\***; values that are not confirmed due to failure to retest or missing lab values will be presumed confirmed:
  - eGFR (by CKD-EPI formula) decrease from Baseline >50%
  - UPCR > 2000 mg/g
  - UACR > 1200 mg/g

\* The Investigator may decide to permanently stop Study Drug based on lesser changes in these parameters observed in isolation or in association with other renal-related abnormalities, taking into account all available and relevant data.

### 8.5.3 Safety Monitoring and Permanent Stopping for Platelet Count Results

All patients will have PLT counts monitored monthly during the Treatment Period. Upon completion of the study Treatment Period, PLTs will be monitored as per visit schedule in [Appendix A](#).

All PLT count results must be reviewed promptly (within 2 business days of receipt) by the Investigator or the designee to ensure that the count has not met a dose interruption or stopping rule. Actions to be taken in the event of reduced PLT count are shown in [Table 2](#).

**Table 2: Actions in Patients with Low Platelet Count**

Platelet Count on Rx	Study Drug	Monitoring
$\geq 100\text{K/mm}^3$	No action	Monitor every month
Below values to be confirmed ideally within 3 days but no later than 7 days	If PLT count is confirmed, follow dosing guidance below:	If PLT count is confirmed, follow monitoring guidance below:
$\geq 75\text{K}$ to $< 100\text{K/mm}^3$	Discussion with Medical Monitor	Closer observation; monitor every 2 weeks 
$\geq 50\text{K}$ to $< 75\text{K/mm}^3$	Pause dosing. When $\geq 2$ successive PLT count values return to $\geq 75\text{K/mm}^3$ restart dosing only if approved by Medical Monitor	Closer observation Monitor every 2-3 days until 2 successive values show improvement Consider discontinuation of anticoagulants/ antiplatelet agents/non-steroidal anti-inflammatory drug (NSAIDs)
$\geq 25\text{K}$ to $< 50\text{K/mm}^3$	Permanently discontinue Study Drug	Closer observation: Monitor daily until 2 successive values show improvement then monitor every 2-3 days until platelet count stable Discontinue anticoagulants/antiplatelet agents/, NSAIDs, while PLT count $< 50\text{K/mm}^3$ if possible Platelet panel to be drawn (Table 3)
$< 25\text{K/mm}^3$	Permanently discontinue Study Drug	Closer observation: Monitor daily until 2 successive values show improvement then monitor every 2-3 days until platelet count stable Steroids and/or IVIG recommended  Consider referral to hematologist Discontinue anticoagulants/antiplatelet agents/NSAIDs medication while PLT count $< 50\text{K/mm}^3$ if possible Platelet panel to be drawn (Table 3)

 Recommended if platelet count decrease / thrombocytopenia cannot be explained by other reasons and is therefore considered drug related.

 Once a patient commences every 2-week monitoring this frequency of monitoring should continue until the platelet count returns to  $\geq 100\text{K/mm}^3$  for 2 successive values.

 The suitability of the patient for reduced (from blinded olezarsen/placebo 80 mg to 50 mg), interrupted and/or continued dosing will be determined by the Investigator in consultation with the Medical Monitor and will be based on factors such as the original rate of decline in the patient's PLT count, whether any bleeding events were experienced by the patient, and the speed of recovery of PLT count after interruption of dosing.

 Recovery in platelet count may be accelerated by administration of high-dose glucocorticoids. Treatment as recommended by the American Society of Hematology (ASH) (2019) guidelines for immune thrombocytopenia (Blood Advances, 10 DECEMBER 2019, Volume 3, Number 23) includes initial therapy with either dexamethasone 40 mg per day for 4 days, or prednisone 0.5 to 2.0 mg/kg per day. Prednisolone or prednisone may be administered for up to 2 to 4 weeks with taper; alternatively, intravenous immunoglobulin (IVIG) may be administered at 0.4 g/kg/d for 5 days, or infusions of 1 g/kg/d for 1-2 days (Provan et al. 2010; Provan et al. 2019).

Any case of a confirmed PLT count reduction to levels below 50,000/mm^3 accompanied by a MB event or CRNMB event, or PLT count of < 25,000/mm^3 independent of a MB or CRNMB event, is considered an adverse event of special interest (AESI) and should be reported following the same requirements as for SAE reporting (Section 9.4.1).

The following (Table 3) is a list of lab analyses that should be performed for any patient with an occurrence of confirmed PLT count less than 50,000/mm^3 during this study. Archived samples prior to Day 1 of investigational treatment may also be analyzed in order to determine the patient's baseline conditions.

**Table 3: Platelet Panel**

To Be Performed at Local Lab
Peripheral smear (should be performed locally, fixed, and sent to central lab for review)
Fibrinogen split products or D-dimer on fresh blood
EDTA sample for PLTs
To Be Performed at Central Lab
Coagulation panel (PT/INR, aPTT)
CBC with reticulocytes and mean platelet volume
Total globulins: IgG and IgM
Complement: total C3, total C4, C5a
Serology for: HBV, HCV, HIV
To Be Performed at Specialty Lab(s)
Antiplatelet antibodies
Anti-ASO antibody

Note: In addition, these labs may also be performed in the event of a platelet count less than 75,000/mm^3 after discussion with the Study Medical Monitor. Additional lab tests may be considered in order to ascertain potential causative conditions for significant platelet count decreases / thrombocytopenia.

#### **8.5.4 Safety Monitoring and Permanent Stopping Rules for Bleeding Events**

Patients will be evaluated for occurrence of bleeding events continuously after the start of Study Drug treatment (Day 1) up to the end of the Follow-up Period. All bleeding events are considered AEs and reported on the AE case report form.

If a MB or CRNMB event occurs (as defined below), the Investigator must notify the Medical Monitor (or designee) and the patient should be treated, as needed, immediately and closely monitored (vital signs, lab tests such as hemoglobin (Hb), hematocrit (HCT), and PLT count, additional visits, overnight stays and coagulation tests may be needed if deemed appropriate by the treating physician) throughout the Treatment and Post-Treatment Evaluation Periods and an (S)AE case report form will be completed. In addition, approximately 2 mL of K2EDTA anticoagulated blood will be collected and resulting plasma must be stored allowing for a centralized assessment of olezarsen concentrations.

If a minor bleeding event occurs, the Investigator should notify the Medical Monitor (or designee) and additional testing of coagulation parameters (aPTT, PT, INR), PLT count, and PLT volume may be performed.

Major bleeding is defined as 1 of the following (Schulman and Kearon 2005):

1. Fatal bleeding
2. Symptomatic bleeding in a critical area or organ, such as intracranial, intraspinal, intraocular, retroperitoneal, intraarticular if in a major joint, or pericardial, or intramuscular with compartment syndrome
3. Clinically overt bleeding leading to transfusion of  $\geq 2$  units of packed RBCs or whole blood or a fall in Hb of 2.0 g/dL (1.24 mmol/L) or more within 24 hours

Clinically relevant non-major bleeding is defined as any sign or symptom of hemorrhage (e.g., more bleeding than would be expected for a clinical circumstance, including bleeding found by imaging alone) that does not fit the criteria for MB but does meet at least 1 of the following criteria (Kaatz et al. 2015):

1. Requiring medical intervention by a healthcare professional
2. Leading to hospitalization or increased level of care
3. Prompting a face to face (i.e., not just a telephone or electronic communication) evaluation

Minor bleeding events are those that do not fulfill the criteria for MB or CRNMB events (defined above), for example excess bruising, petechiae, gingival bleeding on brushing teeth.

**In the event of MB or CRNMB as assessed by the Investigator, and in the absence of any alternative explanation for the cause of bleeding dosing of a patient with Study Drug (olezarsen or placebo) may be interrupted or stopped permanently.** The follow-up schedule for any events meeting this stopping criterion will be determined, including the suitability of the patient for resumption of dosing by the Investigator in consultation with the Medical Monitor (or designee).

### 8.5.5 Safety Monitoring for Constitutional Symptoms

Patients will be instructed to promptly report any signs or symptoms of fever, constitutional symptoms, rash, arthralgia or joint swelling that may arise during the study and the Investigator should closely evaluate all potential causes, including concomitant illness. Patients who experience persistent or increasing symptoms should be tested for ADA and discussed with the Medical Monitor or designee to determine whether additional monitoring or laboratory tests are required.

### 8.5.6 Safety Monitoring for Potential Hypersensitivity Reactions

Patients will be instructed to promptly report any signs or symptoms of potential hypersensitivity reactions including: urticarial rash, pruritus, flushing, angioedema, dyspnea, and/or acute onset hypotension, that may arise during the study. The Investigator should closely evaluate all potential causes, including concomitant illnesses. Patients who experience symptoms of a potential hypersensitivity reaction should be tested for ADA and be discussed with the Medical

Monitor or designee to determine whether additional monitoring or laboratory tests are required. If a hypersensitivity reaction is established, study drug discontinuation should be recommended. The patient's symptoms should be managed per standard of care.

### **8.5.7 Safety Monitoring for Triglyceride and Apolipoprotein B Elevations**

Triglycerides (TG) will be monitored for safety every 3 months. If the measured triglyceride level either (a) in patients with Baseline TGs < 500 mg/dL subsequently exceeds 880 mg/dL or (b) in patients with Baseline TGs  $\geq$  500 mg/dL and < 2000 mg/dL subsequently exceeds 2000 mg/dL and increases by at least 10% from Baseline or (c) in patients with Baseline TGs  $\geq$  2000 mg/dL subsequently increases by at least 30% from Baseline, the site will be notified to contact the patient by phone as soon as able, and no later than their next monthly visit or phone call, to counsel the patient on dietary, lifestyle and medication compliance, and educate and assess the patient for signs and symptoms of pancreatitis. To maintain the blind, the same notification will be provided for an additional patient in the other treatment group using pre-defined criteria to balance the frequency of alerts for both treatment groups, active and placebo. If the TG value remains persistently high at the next regularly scheduled TG safety assessment, a qualified individual, ideally not associated with that subject's assessment, will be informed of the TG value to evaluate and manage the patient's TG levels, moving forward throughout the study, ideally independent of the Investigator's and Study Coordinator's knowledge.

Given the potential for LPL inhibition to change the distribution of cholesterol on lipoproteins, without necessarily affecting the number of cholesterol-rich lipoproteins, apoB levels rather than LDL-C levels will be monitored for safety at 6 months then every 3 months, consistent with guidelines which recognize apoB as the optimal atherogenic lipid metric ([Mach et al. 2020](#)). If the measured apoB level increases by  $\geq$  20 mg/dL, the site will be notified to counsel the patient at their next monthly visit on lifestyle and medication compliance. To maintain the blind, the same reminder will be provided for an additional patient in the other treatment group, using pre-defined criteria to balance the frequency of alerts for both treatment groups, active and placebo. If the subsequent measurement is still high, then the Investigator will be informed of the apoB value and if clinically indicated based on local SOC, may adjust background lipid lowering therapy, in consultation with the patient, according to patient's ASCVD risk.

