### 3 EXPERIMENTAL PLAN

#### 3.1 Study Design

This is a multi-center, randomized, double-blind, placebo-controlled study done in conjunction with the TIMI Study Group, an academic research organization based at Brigham and Women's Hospital and Harvard Medical School. Eligible patients will enter an approximately 4-week Screening Period (that may be extended to 8 weeks if assessments can't be completed within the 4-week period) that includes an at least 2-week Diet/life-style Stabilization/Run-in Period, and an approximately 2-week Qualification Period. Following Qualification, approximately 152 eligible patients will be randomized 1:1 to Cohort A (50 mg) or Cohort B (80 mg) and each cohort further randomized 3:1 to receive olezarsen or placebo in a 53-week Treatment Period. Patients in Cohort A will receive 50 mg of olezarsen once every 4 weeks or matching volume of placebo (0.5 mL) during Weeks 1-49 of the Treatment Period. Patients in Cohort B will receive 80 mg olezarsen once every 4 weeks or matching volume of placebo (0.8 mL) during Weeks 1-49 of the Treatment Period. The 80 mg dose (blinded olezarsen or placebo) may be adjusted to 50 mg every 4 weeks due to tolerability or safety reasons at any point during the study following consultation with the Sponsor Medical Monitor or designee. Randomization will be stratified by Qualification fasting TG levels of < 500 mg/dL vs. ≥ 500 mg/dL. Following the Week 53 visit, patients will enter the 13-week Post-Treatment Follow-up Period. All endpoints will be evaluated after the last patient has completed the Week 53/ET Visit.

**The patients, Investigators, study staff, and the Sponsor are to remain blinded to lipid data (central and local) starting after the first dose on Day 1 then throughout the remainder of the study or as noted for TG or apoB alerts per Section 8.5.7 of the protocol.**

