#### 3.3 Number of Patients

Approximately 152 patients are planned to be enrolled in this study.

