### 10.2 Sample Size Considerations

With 33 patients in each olezarsen treatment group and 22 in the pooled placebo group, there would be an approximately 80% power to detect a 60% difference between each olezarsen treatment group and pooled placebo group at an alpha level of 0.05 (two-sided), assuming 60% reduction in the olezarsen treatment patients, no change in the placebo patients, and a common SD of approximately 73%. It is estimated that dropout rate is approximately 20%.

Approximately 152 patients will be enrolled in this trial to account for potential early dropouts and to facilitate general safety evaluations.

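### Read literally, one sham lipid alert per real alert under 3:1 randomisation equalises alert counts, not per-patient rates, and leaks part of the blind

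*Combined protocol and SAP*

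**What the plan says.** Protocol Section 8.5.7 sets two lipid safety alerts, one for TG and one for apoB. Each leads to a notice to the site, which then counsels the patient. To keep the blind, the TG rule says that "the same notification will be provided for an additional patient in the other treatment group using pre-defined criteria to balance the frequency of alerts". The apoB rule repeats the device: "the same reminder will be provided for an additional patient in the other treatment group, using pre-defined criteria to balance the frequency of alerts". Balance is to hold "for both treatment groups, active and placebo", so the two doses are pooled for this purpose.

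The criteria themselves appear in neither document. SAP Section 4.1.1 only refers back to Section 8.5.7. The text does not say whether the frequency to be balanced is a count per group or a rate per patient.

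On allocation, Section 3.1 states that "approximately 152 eligible patients will be randomized 1:1 to Cohort A (50 mg) or Cohort B (80 mg) and each cohort further randomized 3:1". The same section keeps patients, investigators, study staff and the sponsor blind to lipid results after the first dose, with these alerts as the exception.

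**The concern.** Both rules describe the sham in the singular, as one more patient per real alert. One-for-one matching gives the two groups the same number of alerts. Because one group is three times as large as the other, it does not give a patient the same chance of an alert in either group. Section 8.5.7 and the 3:1 ratio are both in the protocol that sites hold, so an investigator can work out what an alert implies.

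The blind is what is mainly at stake. The site staff who receive the notice also rate the relationship of adverse events to study drug (Section 9.4.3.1), and they can decide to discontinue study drug (Section 8.7). Under the apoB rule, after a second high value, the investigator may also change background lipid therapy.

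A second, smaller issue is that each alert brings counselling on lifestyle and medication compliance, and on diet under the TG rule. If alerts are more frequent per patient on placebo, so is that counselling. The treatment policy strategy in SAP Section 4.9.2.1 keeps all later values, so any effect would stay in the estimate.

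**Working it through.** The plan gives no alert count, alert rate or explicit sham ratio, so it has no figure of its own to reproduce here. Only the allocation can be checked.

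**Inputs**
- Planned number: 152 (Section 3.3).
- Allocation: 1:1 to cohorts, then 3:1 (Section 3.1). Each cohort has 152/2 = 76 patients, of whom 57 receive olezarsen and 19 placebo. In total, 114 receive olezarsen and 38 placebo.
- Check: Section 10.2 uses 33 + 33 = 66 olezarsen and 22 placebo, also 3:1.
- Real alerts: *a* on placebo and *b* on olezarsen. These are not in the documents, so they are varied as assumptions.
- Every real or sham alert is taken to reach a different patient.

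**One sham per real alert**
- Alerts on placebo: *a* + *b*. Alerts on olezarsen: *b* + *a*.
- Per-patient rates: (*a* + *b*)/38 and (*a* + *b*)/114. Their ratio is 114/38 = 3.0.
- P(placebo | alert) = (*a* + *b*)/[2(*a* + *b*)] = 50%.
- Prior: 38/152 = 25%. The odds move from 1:3 to 1:1, a likelihood ratio of 3.

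Neither result depends on *a* or *b*.

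**Shams in the randomisation ratio** (three olezarsen shams per placebo alert; on average one-third of a placebo sham per olezarsen alert)
- Alerts on placebo: *a* + *b*/3. Alerts on olezarsen: *b* + 3*a* = 3(*a* + *b*/3).
- The alerts split 1:3, as the patients do. The rate ratio is 1.0 and P(placebo | alert) is 25%.

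**Scenarios** (rates are placebo vs olezarsen; the percentage in brackets is P(placebo | alert))

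| Real alerts (*a*, *b*) | No shams | One-for-one | Randomisation ratio |
|---|---|---|---|
| 4, 0 | 10.5% vs 0% (100%) | 10.5% vs 3.5% (50%) | 10.5% vs 10.5% (25%) |
| 6, 2 | 15.8% vs 1.8% (75%) | 21.1% vs 7.0% (50%) | 17.5% vs 17.5% (25%) |
| 2, 6 | 5.3% vs 5.3% (25%) | 21.1% vs 7.0% (50%) | 10.5% vs 10.5% (25%) |
| 1, 9 | 2.6% vs 7.9% (10%) | 26.3% vs 8.8% (50%) | 10.5% vs 10.5% (25%) |

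In the first two rows the one-for-one sham dilutes a strong signal. In the third row the true per-patient rates are equal and the sham creates the imbalance. In the fourth it reverses the direction. The absence of an alert says little: with *a* = 4 and *b* = 0, P(placebo | no alert) = (38 − 4)/(152 − 8) = 34/144 = 23.6%.

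**Timing of counselling against the Month 6 endpoint** (average of Weeks 25 and 27)
- ApoB is first checked at 6 months, with counselling at the next monthly visit. An alert from the Week 25 sample therefore leads to counselling at about Week 29, after the endpoint is measured.
- TG is checked every 3 months, so essentially only the Month 3 check can lead to counselling in time.
- Appendix A already recommends diet, lifestyle and alcohol counselling for every patient at run-in and at Weeks 1, 5, 13, 21 and 25.

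**The case against.** The strongest objection is that one-for-one matching is inferred from a singular noun. The same sentence appeals to pre-defined criteria that balance frequency. Those criteria are not published, and frequency can mean a rate per patient, so they may already allow for 3:1. This stands as a limit on confidence. It does not remove the point, because rate-balancing criteria would need about three olezarsen shams per placebo alert and a placebo sham for only about a third of olezarsen alerts. Neither fits a rule of one more patient per alert. Either the ratio misses its aim or the sentence misdescribes the algorithm.

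Three stronger readings are tempting, and the documents do not support them:
- **That an alert reveals placebo.** It does not. The probability rises to an even chance, and where real alerts are all on placebo the sham lowers it from 100% to 50%.
- **That placebo patients have three times the alert rate to begin with and the sham fails to correct it.** The ratio before shams depends on true rates that nobody has stated. The factor of 3 is a product of the one-for-one rule.
- **That the primary endpoint is materially biased.** The apoB rule acts too late under its schedule. The TG rule adds one contact to counselling already planned for everyone. Extra counselling on placebo would tend to lower placebo TG and shrink the treatment difference, which is conservative for the primary test. The endpoint is a laboratory value, and the results are otherwise withheld from sites.

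**Conclusion.** The point holds as a cheap improvement. On the literal wording, the sham rule equalises counts where its blinding purpose needs equal per-patient rates. The alert rate is then 3.0 times higher on placebo, and P(placebo | alert) is 50% instead of 25%, whatever the true alert rates. The result is a partial leak of the blind to site staff; the arm is not disclosed. Unequal counselling is a secondary matter. For Month 6 it concerns essentially the TG rule, and its size cannot be estimated from the documents.

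The conclusion assumes the planned 114:38 split among patients at risk, a different patient for each alert, and one sham per real alert. Confidence is high for the arithmetic and moderate for the one-for-one reading.

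**What to change.** State in Section 8.5.7 that balance means equal per-patient alert rates on olezarsen and placebo, and replace the singular rule, for both TG and apoB, with shams in the randomisation ratio:
- for each real placebo alert, notify three olezarsen patients;
- for each real olezarsen alert, notify one placebo patient with probability 1/3, decided at random. A fixed one-in-three sequence would leave the first two olezarsen alerts without a sham.

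Alert thresholds and the handling of truly alerted patients stay as they are. If the pre-defined criteria already work this way, only the wording needs correcting, with a reference to where the criteria are kept.

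The cost is a short text change, a setting in the alert algorithm, and two extra counselling contacts on olezarsen per real placebo alert (3 − 1 = 2). Placebo shams fall by two-thirds per real olezarsen alert (1 − 1/3).
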